5. LONG TERM FOLLOW-UP FORM

Long term follow-up v Patient no longer t			/YYYY) Patient identifier ᆜᆜ ib						
Eastern Cooperative C	ncology Group	(ECOG) available							
If yes, □ 0	□ 1 □ 2	□ 3 □ 4 □ 5							
Death ? ☐ Yes	□No								
If yes, Date of death/ (DD/MM/YYYY)									
Cause tumor-related other cause									
Please observe the definitions and AE and serious AE reporting as defined in the protocol									
Has the patient receive	ed any treatmer	nt for mRCC since las	t visit?						
☐ Yes ☐ No									
If yes, please u	pdate the follo	wing table :							
Drug name	Starting date	Status	Reason for discontinuation						
	 //_/_//_//////////////////////	□ Ongoing	☐ Progressive disease						
Line : □ 2 □ 3 □ 4	لللل	□ Discontinued	Date :						
□ 5 □ other :	(MM/YYYY)	End date/ (MM/YYYY)	☐ Intolerance						
			□ other						
Best response									
□ CR □ PR □ SD □									
PD 🗆 NA									
		□ Ongoing	□ Progression disease						
	(MM/YYYY)	□ Discontinued	Date :/						
Line : □ 2 □ 3 □ 4	(End date/	□ Intolerance						
□ 5 □ other :		ーコーコ (MM/YYYY)	□ other						
Best response									
□ CR □ PR □ SD □									
PD 🗆 NA									
(new lines can be added		nes are received) (Not A	assessable)						
Occurrence of adverse									
Has the patient experience			□ Yes □ No						
sections are still editable			lready available ; the pre-completed						
The safety requirement a	s described in th	e protocol are reminde	d via a click)						

ADONIS CRF Subject ID:

Please complete this form every 6 months until end of the study

ADONIS CRF Subject ID:

6. STUDY DISCONTINUATION

Study Discontinuation
Please complete this form in case of study discontinuation during the study at any time of the study for any reason
Date of study discontinuation : / / (DD/MMYYYYY)
Reason for study discontinuation
☐ Subject did not show up again (e.g. moved away), "Lost to follow-up",
☐ Subject was enrolled in another clinical study
☐ Subject's request / withdrawal of subject's consent
□ Death
☐ Other, please specify :
If the patient is alive at study discontinuation:
Date of the last visit with the patient at the site / / (DD/MM/YYYY)
If the patient was treated with Sunitinib / Axitinib* at the previous visit :
Sunitinib /Axitinib* status at the last visit date : □ Ongoing □ Discontinued
End date / (MM/YYYY)
Reason for discontinuation
□ Progression disease Date : ᆜᆜ / ᆜᆜ / ᆜᆜ ᆜ
□ Intolerance
□ other
*: name to be selected according to the line of the treatment
In case of death 2 Voc No.
In case of death ?
Date of death
Cause tumor-related other cause
If the patient was treated with Sunitinib / Axitinib* at the previous visit:
Sunitinib / Axitinib* status at the date of death : □ Ongoing □ Discontinued End date □□ / □□□□ (MM/YYYY)
Reason for discontinuation
☐ Progressive disease Date : ☐ / ☐ / ☐ ☐ Intolerance
□ other
*: name to be selected according to the line of the treatment
. Have to be delected describing to the line of the treatment

ADONIS CRF

Subject ID:

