8.1. Study design

8.1.1. Global design

ADONIS is an international (EU), prospective (partly retrospective), non-interventional, non-controlled, observational multicenter study.

Patients can be enrolled from several EU countries including Austria, Belgium, Denmark, France, Finland, Germany, Greece, Ireland, Italy, Norway, Portugal, Spain, Sweden, Switzerland, The Netherlands and UK (non-exhaustive list).

Investigators will be specialists in charge of adv/mRCC. The sites involved (at least when performing feasibility) will be representative of their respective country in terms of practice. Participating physicians will not be influenced in their decision making and routine proceedings in any way.

The study will enroll approximately 750 adv/mRCC patients at the 1st and 2nd line treatment level. Patients will be enrolled when they start a treatment with SU in 1st line or AXI in 2nd line post SU treatment.

Patients enrolled at SU initiation, will be followed-up whatever the post SU 2nd line treatment is (AXI, other drugs, no further active treatment, (supportive care)). The possible 1st and 2nd line sequences of treatment under investigation (i.e. patient pools) are (Figure 1):

- SU (prospective) AXI
- SU (retrospective) AXI
- SU not further active treatment (supportive care)
- SU other second line treatment (sorafenib, pazopanib, everolimus, temsirolimus, other)

[figure not shown]
The study will include a retrospective and/or prospective data collection period:

- Retrospective data, consisting of SU 1st line treatment records, will be collected for patients who start the study with AXI in 2nd line.
- Prospective data in terms of medical treatment records, will be collected for all 2nd line AXI patients.

Prospective data will also be collected for all patients enrolled in the study at the SU 1st line level, irrespective of 2nd line treatment, or no further active treatment.

The inclusion period of eligible patients is planned for 54 months, with a minimum 2-year follow-up period. Patients will be followed-up from their enrollment to the end of the study follow up period.

Figure 1: study flow chart

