8.2. Setting

The study will enroll patients according to the eligibility criteria in participating countries across Europe. The recruiting centers will be representative of each country involved in terms of care management systems, of size and of practices (at least when performing feasibility).

Any patient who meets the eligibility criteria will be invited to participate in the study with no selection by the investigators. The enrollment visit will be performed at the time of the patients' inclusion, after the patients' acceptation of enrollment in the study.

Data will come from medical records and will be collected in routine clinical practice. The enrollment visit will comprise a first section on patients' eligibility for every patient whatever pool they belong to and a second section depending on the treatment started (SU or AXI) at the inclusion.

For patients enrolled in the study when AXI is started as a 2^{nd} line therapy, a retrospective section will be completed at patients' inclusion, to collect data on SU 1^{st} line treatment.

For patients who start AXI when SU is discontinued during the study, the AXI initiation visit will resume baseline data that need to be updated.

Follow-up will be ensured during visits in the context of usual patients' care management (non-interventional study). No visits will be required by the protocol of the study. As long as the

patients are treated with SU or AXI, every visit to the center will be recorded. In accordance with ESMO guidelines and physicians clinical practice is real life, follow-up visits are approximately expected:

- during SU treatment: every 6 weeks (every cycle) with tumor assessment approximately every 3 months with respect to the clinical practice
- during AXI treatment: every 4 weeks (every cycle) with tumor approximately assessment every 2 months with respect to the clinical practice

[figure not shown]
When patients come off SU treatment (i.e. are not receiving AXI) or come off Axitinib (after receiving the SU-AXI sequence) they will be followed up every 6 months (separate form) for survival until the end of the study.

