Data will come from medical records and will be collected in routine clinical practice. Because of the inclusion criteria (Patients being treated with SU in 1st line according to the European therapeutic indication and/or being treated with AX! in 2nd line according to the European approved therapeutic indication (except post cytokines)) the medication is prescribed within the regular practice of the physician. As a non-interventional study, there are no specific requirements with regards to the treatment process.

The study will include:

- a retrospective data collection period consisting of SU 1st line treatment records for patients who start the study with AXI in 2nd line;
- *A prospective data collection period for all patients enrolled in the study (sociodemographic, treatment and medical data).*

The medical data collection methods used will be:

- *eCRF* (*electronic Case Report Form*) for physicians;
- Paper questionnaires for patients (assessment of the quality of life).

The Quality Of Life questionnaire will be completed at baseline and then every month for patients receiving AXI. QoL will also be measured at the discontinuation of AXI treatment. The physician will remit the QoL questionnaire to the patient and ask him/ her to complete it every month at home (i.e. Day 0 Day 30 Day 60 etc.). Patients will return it using pre-stamped envelopes. If not done before, the questionnaire will be completed at the site preferentially prior to the follow-up visit(s).

[figure not shown]
Observation period:

Patients will be enrolled for 3 years and followed-up for a minimum 2-year period, until the end of the study, whatever the therapeutic strategy post SU or post AXI. Visits will be naturalistic but follow-up visits are approximately expected:

- *during SU treatment: every 6 weeks (every cycle) with tumor assessment approximately every 3 months with respect to the clinical practice;*
- *during AXI treatment: every 4 weeks (every cycle) with tumor approximately assessment every 2 months with respect to the clinical practice;*

When patients come off SU treatment (i.e. are not receiving AXI) or come off AXI (after receiving the SU-INL sequence) they will be followed up every 6 months (separate form) for survival until the end of the study.

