The OS will be defined as the time from date of first SU dose to the date of death of any cause. For patients not experiencing the event, their survival times will be censored at the last date they are known to be alive

Variable name	Definition
OS status	Patient will not be censored for the OS analysis (OS status = 1) in the following cases:
	1) Axitinib discontinued due to Death (cf. CRF page 35)
	2) Death reported in Long term Follow-up (cf. CRF page 36)
	 Death reported on the Study Discontinuation form (cf. CRF page 37)
	In all other cases, patient will be censored for the OS analysis (OS status $= 0$).

OS status and OS time will be calculated as detailed below:

Variable name	Definition					
OS time	The overall survival time will be calculated in months as:					
(months)	 (Date of death reported at time of Axitinib discontinuation - Start date of Sunitinib + 1) / 30.44, if case n°1 described above is reported 					
	 (Date of death reported in Long term Follow-up - Start date of Sunitinib + 1) / 30.44, if case n°2 described above is reported 					
	 (Date of death reported on the Study Discontinuation form - Start date of Sunitinib + 1) / 30.44, if case n°3 described above is reported 					
	Else, the overall survival time will be censored as follows:					
	 (Maximum of {All visits dates reported} - Start date of Sunitinib + 1) / 30.44 					
	Note: Start date of Sunitinib will be the one reported:					
	- at time of Sunitinib initiation visit for patients enrolled at SU initiation (cf. CRF page 11 " Therapy started with Sunitinib in 1st line on ")					
	- at time of Axitinib initiation visit for patients enrolled at AXI initiation (cf. CRF page 26 "Therapy started with Sunitinib in 1st line on")					

- Best Response under Axitinib in 2nd line post Sunitinib

Number and percentages of patients by best response (CR, PR, SD or PD) will be presented.

- Objective Response Rate (ORR) under Axitinib in 2nd line post Sunitinib

ORR is defined as the percentage of patients with complete response (CR) or partial response (PR) according to RECIST from the start to the end of Axitinib treatment (cf. CRF page 29).

Patients who die, progress, or drop out for any reason prior to reaching a CR or PR will be counted as non-responders in the assessment of ORR.

All assessments following an assessment of PD will be excluded from the derivation of ORR.

- Clinical benefice Rate (CBR) under Axitinib in 2nd line post Sunitinib

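### The discontinuation form accepts entry into another study as an exit from this one and collects no later vital status, so overall survival may be informatively censored

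*Protocol*

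**What the plan says.** Four places promise follow-up to the end of the study:

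- Protocol 8.1.1 (Global design): "Patients will be followed-up from their enrollment to the end of the study follow up period".
- Protocol 8.2 (Setting), on patients who have come off sunitinib without starting axitinib, or have come off axitinib: "they will be followed up every 6 months (separate form) for survival until the end of the study".
- SAP 2.1 carries follow-up "until the end of the study, whatever the therapeutic strategy post SU or post AXI".
- The long-term follow-up form (Annex 1, CRF section 5) is due every six months to study end. It has rows for later treatments by line.

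The Study Discontinuation form (Annex 1, CRF section 6) is to be used as follows: "Please complete this form in case of study discontinuation during the study at any time of the study for any reason". Its printed reasons are loss to follow-up, "Subject was enrolled in another clinical study", the patient's request or withdrawal of consent, death, and other. For a patient who is alive it asks for "Date of the last visit with the patient at the site" and for drug status. It has no field for survival after that date.

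SAP 6.1.2 counts a death for sequence OS if it appears on the axitinib discontinuation page, the long-term form or the discontinuation form. Otherwise it censors at "Maximum of {All visits dates reported} - Start date of Sunitinib + 1) / 30.44". The same censoring rule is given for OS from first-line sunitinib.

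**The concern.** In a non-interventional study, joining another study does not by itself prevent a site from recording whether the patient is alive. The form lists it separately from consent withdrawal, and Protocol 9.2 bars further data only when consent for future information is also withdrawn. The form therefore offers an avoidable exit.

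Kaplan-Meier treats a censored patient as having the same future hazard as those still at risk. Patients who enter another study may be fitter than that group. They may also have just failed a treatment, which would put them at higher risk. Either difference would bias median and 24-month OS for the SU-AXI sequence. SAP section 7 offers only the general remark, written for the primary endpoint, that survival analysis copes with missing data through censoring. No OS sensitivity analysis is planned.

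The SAP also treats this exit differently across endpoints. Where axitinib is the last treatment, its TTF rules count study discontinuation as an event unless the reason is loss to follow-up or the patient's request. One tick can therefore be a failure for a primary endpoint and a censoring for OS.

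**Working it through.** **Step 1. Is there a conflict?** The follow-up passages contain no exception for patients in another study. Neither the eligibility criteria (8.2.1, 8.2.2) nor the withdrawal section (9.2) makes it a ground for leaving. Section 9.2 says that stopping treatment or being lost to follow-up is not withdrawal, and it does not mention another study. Only the form supplies this exit.

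**Step 2. What happens to OS?** A living leaver with no later form has a last visit date and no later date. The SAP maximum over visit dates then censors at that visit. If a later long-term form is filed, its date or death is used.

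**Step 3. The plan's nearest figure.** The documents give no OS sample size and no share of leavers. The nearest stated precision is in Protocol 8.5, for PFS and TTF at the median with n = 350: 1.96 × √(0.25/350) = 0.0524, stated as 5.2%. It reproduces and serves here only as a yardstick.

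**Step 4. Size, from assumed inputs.** In each model, Kaplan-Meier OS with censoring at exit is compared with OS under full follow-up. Shifts are the former minus the latter.

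- Model A: constant hazard, median OS 20 or 30 months, exit at 8–24 months if alive.
- Model B: time from first sunitinib dose to axitinib stop is gamma (shape 2, scale 9 months); exit is 0.5 month after axitinib stop; median survival after axitinib is 8, 12 or 16 months; administrative censoring is uniform over 24–84 months; nobody dies on axitinib.
- Model C: as B, but with a death hazard on axitinib of 25–50% of the later hazard.

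| Model | Marked to leave | Hazard of leavers vs others | 24-month OS, points | Median OS, months |
|---|---|---|---|---|
| A | 5–20% (3–14% do leave) | 0.5–1.5 | −1.3 to +1.1 | −1.7 to +1.2 |
| B | 5–15% | 0.5–0.85 | +0.1 to +2.5 | −0.4 to +1.1 |
| B | 5–15% | 1.0 | +0.6 to +3.0 | +0.4 to +1.3 |
| C | 5–15% | 0.5–1.0 | −0.7 to +1.6 | −0.5 to +0.8 |

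A repeat run of C gave −0.8 to +1.5 points and −0.4 to +0.8 month, so its bounds are good to about 0.1.

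**Step 5. One case by hand** (Model A, median 30 months, 20% marked, hazard ratio 0.5). The hazard is ln 2/30 = 0.0231 per month.

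- Not marked: 24-month survival is 0.5^(24/30) = 0.574. Kaplan-Meier with exit censoring estimates this value.
- Marked: e^(−12×0.0231) × [e^(−0.0924) − e^(−0.2773)]/0.1848 = 0.758 × 0.832 = 0.631.
- Full follow-up: 0.8 × 0.574 + 0.2 × 0.631 = 0.586.
- Shift: 0.574 − 0.586 = −0.011 after rounding, or −1.1 points.

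**Step 6. Why the sign varies.** In Model A the shift is zero at a hazard ratio of 1.0, because exit timing cannot matter under a constant hazard. In B and C exit comes when the hazard rises, so leavers are represented partly by patients still on axitinib, and OS is pushed up even at a ratio of 1.0. Fitter leavers pull it back down.

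**The case against.** A reader might infer that the form orders patients out and so ends their survival follow-up. It does not: it records the reason for an exit that has happened. Protocol 9.2 asks for every effort to document outcome after any withdrawal, and the long-term form makes no exception for patients in another study. This stands in part, but the request in 9.2 holds only where possible, and no form exists for outcome after exit.

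A reader might also infer that OS is informatively censored as a matter of fact, or that it would describe only patients who never joined another study. The documents support neither. Leavers count in the risk set until they are censored, and bias needs a later hazard that differs from that of patients still at risk. That is plausible but not shown. Nor does the SAP contain a rule to censor at trial entry; the censoring follows from the absence of later forms.

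Shifts of 2.5 to 3 points in 24-month OS should not be relied on. They come from Model B, in which nobody can die on axitinib, although death is a listed reason for stopping it. With equal hazards before and after axitinib stop and fitter leavers, the 24-month shifts were all negative.

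Finally, OS is secondary and descriptive, and the shifts are small beside sampling error. That is right, but the confidence interval reports sampling error and would not show this bias.

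**Conclusion.** The conflict between the form and the promised follow-up is real and rests on the documents alone. Its effect on OS is possible but unquantified, because the documents give neither the number of leavers nor their prognosis. Under Model C the shift is about −0.7 to +1.6 points in 24-month OS and −0.5 to +0.8 month in median OS, with no fixed direction. The larger bound is about three tenths of the 5.2-point yardstick (1.6/5.2 = 0.31). Every model input is assumed, and Model A gives a wider range for the median. This is a low-severity point, worth acting on because the remedy is cheap.

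**What to change.** - State on the discontinuation form and in Protocol 8.2 and 9.2 that entry into another study ends at most the treatment-period data and is not a study exit.
- Record entry into another study as an item on the long-term follow-up form, so that it can be counted. Deleting the tick-box alone would only move these exits to the free-text other category.
- Continue the existing 6-monthly survival form until death, withdrawal of consent for further data, or study end.
- For patients already discontinued for this reason, collect vital status where consent allows.
- Report the number of such exits, with one OS sensitivity analysis.

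The cost is an eCRF edit, a site instruction and a few more 6-monthly forms. If the eCRF can no longer be changed, the last two steps remain possible.

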ANNEX 2: ADVERSE EVENT REPORT FORM

Subject ID:

Non Interv	entional Stud	ly Adver	se Eve	nt Report F	Form				Г		F 55			_
			AFR #	(insert when kno	energi				$\neg \vdash$	Locals	For Pfizer i #		Reported	
Pfizer			721		, any				7				-	
PROTOCOL#		'		SUBJECT#								_		
Protocol Title:														
☐ Initial Report [Follow Up Re	eport		Col	untry	where (event	occurr	ed:					
Dat Patient Data	te of Birth			ioity: Asian r(specify)		Black []	lispanio			per local		White _	
	Male 🗌 Female	9	Weight		lb [kg		Height	1		in	Cf	m	
If patient Date has died:	of Death Ca	use(s) of	Death	Determin					_	nown De	eath:			
Patient History	Provide rel	levant me	dical hic	otory below In								-oxic	etina med	lical
☐ None ☐ Unknown				ice is necess									-	
liness (spe	Date	Stop Date		ek bax ngoing			Include		ent Detaik wooedure		d dates			
					[
					[
					[
Study Drug (Trade Ros	e and Generic) ute, Indication	, Formula	ition,	Check box If Pfizer Drug	ı	Dose		Units	Fre	Frequency		T	Stop Date	Check box if Ongoing
												Т		
												T		
							\top					T		
												T		
Concomitant Druge None Unknown	more than	two week	ks befor	gs taken with re the event, dditional copie	and ar	ny drug	used							
Drug Name (Trade	and Generic)			Reaso	on for	Use			Route		Start Date	T	Stop Date	Check box if Ongoing
												\perp		
							\perp					\perp		
Relevant Tests				matory test re page io negeo							nple, from	bloc	od tests, d	liagnostic
Test	Result		Uni	ts	Normal Panne			gh	Comments					
											\perp			
											\perp			
											\perp			

Version3 .May2012

Subject ID:

Non Interv	eport I	Form				For Pfizer internal use only							
	t when inc	num)				Loc	cal#	Date Reported to Pfizer					
Plizer		7.2			, may								
PROTOCOL#			SUB	JECT#	: [
	P	DVERSE EVE	NTS (ii	more th	an two	use ac	lditiona	copieso	f this pag	e)			
		Specify di											
Adverse Event Ten	m					Adverse Event Term							
Onset Date:		_			- 1	Onset D				_			
Is the event seriou If yes, identify serio		_	□ No	•				rious? seriousr	ness crite	eria belo	Yes No		
If yes, identify seriousness criteria below: Seriousness Criteria (Check all that apply): Resulted in death Ufe-threatening Hospitalization/Prolongation of hospitalization Persistent/Significant disability/Incapacity Congenital anomaly/Birth defect						Serious Resu Life- Hosp Pers	sness (ulted in threate bitalizat istent/S genital	Criteria (C death	heck all ngation of disability Birth defe	that app hospita	ply): lization		
Status at date of report or at death: Date of Recovered Recovery: Recovered with sequelae Recovering Not Recovered Unknown						Status at date of report or at death: Date of Recovered Recovery: Recovered with sequelae Recovering Not Recovered Unknown							
Is there a reasonal Study Drug Yes		that the event	is relat	ed to		Is there a reasonable possibility that the event is related to Study Drug ☐ Yes ☐ No							
If yes, specify \$tud	ly Drug:				_ [·	If yes, specify Study Drug:							
					Щ.								
Is there a reasonal Concomitant Drug			is relat	ed to		Is there a reasonable possibility that the event is related to Concomitant Drug Yes No							
If yes, specify Con	comitant Drug	E				If yes, s	pecify	Concom	itant Dru	g:			
Last Drug Action T	aken During E	vent(s), speci	fy drug	name:		Last Dr	ug Act	ion Takeı	n During	Event(s), specify drug name:		
Withdrawn (tem) or permanently, or d Dose reduced Dose increased Dose not change Unknown Not applicable	elayed)	Withdrawn or permanently Dose redu Dose incre Dose not c Unknown Not applica	or dela ced ased hanged ible	yed)		Dos Dos Unk	anently e reduce e incre e not co nown	ased hanged ble	ed)	Or per	(ithdrawn (temporarily manently or delayed) ose reduced ose increased ose not changed nknown ot applicable		
Did an SAE/AE recur				Yes		No		Unkn	own	No	t Applicable		
	If yes, which S	AE(s)/AE(s):											

Subject ID:

Non Interventional Study Adverse Event Report Form For Pizer internal use only														
O.C.		AEI	R# (inser	t when ki	ючт)					Local	#	Date	Reporte	d to Pfizer
Plizer														
PROTOCOL#	•		SUB	JECT:	#									
Event Narrative														
Provide any informa If additional space is						sis and	treatn	nent of	the eve	nt(s) not	otherw	ise repo	rted on	this form.
Reporter Commen	ts:													
Reporter:														
Fir	st Name			La	st Name	(Plea	se PRI	NT)			D	ate: DD-	MMM-Y	YYY
Address:					1									
9:	reet			Cit	ty / State	=			Zip Co	de	O	ountry		
Telephone:			Fax:						En	nail:				
Investigator's Nam	ie:				In	vestig	ator (d	or Desi	ignee) .	Awarene	ss Dat		- MMM-Y	YYY
Investigator or Designee Signature :														

Subject ID:

